7.3.3 Further endpoint analyses

Further time-to-event endpoints will be analysed in the same Cox proportional hazards model as the primary analysis.

Change from baseline to 30 days after treatment stop of eGFR (CKD-EPI)_{cr} will be evaluated by an ANCOVA model, including treatment group, gender, geographical region, baseline LVEF, and history of DM as fixed effects and baseline eGFR (CKD-EPI)_{cr} (continuous) and age (continuous) as linear covariates.

An unmatched win ratio considering adjudicated CV death and adjudicated HHF will be analysed based on unmatched pairs. All patients randomised to empagliflozin will be compared to all patients randomised to placebo. Only common follow-up time will be considered for the comparison. Patients on empagliflozin are considered to have “won” the comparison if either the other patient has died while the patient on empagliflozin was still alive, or if both patients did not die, then if the other patient had more occurrences of HHF, or if the number of occurrences of HHF is the same but the time to the first occurrence of HHF is longer. The number of comparisons won is noted as N_W . Patients on empagliflozin are considered to have “lost” the comparison if the empagliflozin patient died while the patient on placebo was still alive, or if both patients did not die, then if the patient on empagliflozin had more occurrences of HHF, or if the number of occurrences of HHF is the same but the time to the first occurrence of HHF is shorter. The number of comparisons lost is noted as N_L . The win ratio is N_W / N_L .

The rules for winning and losing follow a modified Rogers 2014 [[R16-4909](#)] approach also considering the time to the first HHF event in case of a tie on the number of HHF events. The analysis of the unmatched win ratio will be conducted as described in Pocock 2012 [[R16-4813](#)].

Further longitudinal continuous endpoints will be analysed in a mixed model with repeated measures (MMRM), including age and eGFR (CKD-EPI)_{cr} at baseline as linear covariates and visit by treatment interaction, baseline by visit interaction, geographical region, gender, baseline LVEF, and baseline history of DM as fixed effects.

The details of analyses will be defined in the TSAP prior to unblinding.

7.3.4 Safety analyses

In general, safety analyses will be descriptive in nature and will be based on BI standards. Standard BI summary tables and listings will be produced. No hypothesis testing is planned. Statistical analysis and reporting of adverse events will concentrate on treatment-emergent adverse events. To this end, all adverse events occurring between start of treatment and end of the REP will be considered ‘treatment-emergent’. The REP is defined as 7 days after last dose intake. Adverse events that start before first drug intake and deteriorate under treatment will also be considered as ‘treatment-emergent’. Frequency, severity, and causal relationship of adverse events will be tabulated by system organ class and preferred term after coding according to the current version of the Medical Dictionary for Drug Regulatory Activities (MedDRA).

Laboratory data will be analysed both quantitatively as well as qualitatively. The latter will be done via comparison of laboratory data to their reference ranges. Values outside the reference range as well as values defined as clinically relevant will be highlighted in the listings. Treatment groups will be compared descriptively with regard to distribution parameters as well as with regard to frequency and percentage of patients with abnormal values or clinically relevant abnormal values.

Vital signs (blood pressure, pulse rate), physical examinations or other safety-relevant data observed at screening, baseline, during the course of the trial and at the end-of-trial evaluation will be assessed with regard to possible changes compared to findings before start of treatment.

Reasons for discontinuation and use of post-baseline concomitant medications will be tabulated.

The details of the analysis will be specified in the TSAP.

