#### **7.8.1.1 Assignment of AEs to treatment**

The analysis of adverse events will be based on the concept of treatment emergent adverse events. That means that all adverse events occurring between first drug intake till 7 days after last drug intake will be assigned to the randomised treatment. All adverse events occurring before first drug intake will be assigned to 'pre-treatment' and all adverse events occurring after last drug intake + 7 days will be assigned to 'follow-up'.

In Section 15.3 general AE analyses tables will present only on-treatment AEs (applying the rule of 7 days for assignment as on-treatment) for the treatments groups (exceptions for urinary tract malignancies, hepatic events, lower limb amputations and bone fractures as well as adjudicated events see below). When looking at BICMQs or standardized MedDRA queries (SMQs) and including all AEs up to completion of the trial, the time at risk for each patient will be calculated up to the individual day of trial completion (see [section 6.8](#)).

Appendix 16.1.13.1 will include an analysis (overall summary table, frequency of AEs by system organ class (SOC) / preferred term (PT), frequency of serious adverse events (SAEs) by SOC/PT) where AEs and SAEs are assigned to the following phases: Screening, each

treatment group, post-treatment for each treatment group.

The tables presenting frequency of AEs by SOC/PT and frequency of SAEs by SOC/PT will be repeated in Section 16.1.13.1 with treatment-specific post-treatment phase included, hereby also incidence rates for the post-treatment phase will be presented.

For listings, AEs will be assigned to one of the treatment phases of Screening, Placebo, Empa 10, Placebo post-treat, Empa 10 post-treat, post-study.

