7.8.1.7 Adverse event incidence rates

In addition to the frequency tabulations, time-adjusted adverse event analyses will be performed for all AEs, investigator defined drug-related AEs, AEs leading to discontinuation, serious AEs, and adverse events of special interest by SOC, respectively HLT, and PT.

The time at risk in patient years for the on-treatment phase is derived as follows:

Patients with AE:

time at risk (AE) in days = date of start of AE with specified PT/SOC/HLT – study treatment start date + 1

Patients without AE:

time at risk (AE) in days = end date of time at risk – study treatment start date + 1, where end date of time at risk is the minimum of date of last study drug intake + x days and date of death, if applicable.

The standard approach will be x=7 days, but for certain AESIs in addition other approaches will be used.

Total AE-specific time at risk per treatment group is then derived as:

Time at risk (AE) [years] = Sum of time at risk [days] over all patients in a treatment group / 365.25

For 'each row of a table' (e.g. displaying an SOC), time at risk is calculated using start of first AE summarized in this row; e.g. for patient with AE in a specified SOC, time at risk = date of start of AE with specified PT in this SOC – start of study treatment + 1.

The AE incidence rate per 100 patient years will then be calculated as follows:

Incidence rate per 100 patient years (pt-yrs) = 100 \* number of patients with AE / time at risk (AE) [years].

In a similar way the time at risk and incidence rate for the post-treatment period is derived. Hereby the start date is the start date of the post-treatment phase instead of the study treatment start date.

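### The SAP drops, without declaring it, the protocol's rule that an AE starting before first drug intake and deteriorating on treatment is treatment-emergent

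*Protocol*

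**What the plan says.** Protocol 7.3.4 gives two routes to treatment-emergent status. The first is by time: "all adverse events occurring between start of treatment and end of the REP will be considered" treatment-emergent, and "The REP is defined as 7 days after last dose intake". The second is by deterioration: "Adverse events that start before first drug intake and deteriorate under treatment will also be considered as" treatment-emergent.

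SAP 7.8.1.1 says that the AE analysis rests on the treatment-emergent concept and then spells out what that means. It gives only the time route: "all adverse events occurring between first drug intake till 7 days after last drug intake will be assigned to the randomised treatment". For earlier events it says: "All adverse events occurring before first drug intake will be assigned to" the pre-treatment category. In Section 15.3 of the trial report, "general AE analyses tables will present only on-treatment AEs". The exceptions it names are urinary tract malignancies, hepatic events, lower limb amputations, bone fractures and adjudicated events; deterioration is not among them. An appendix display is also planned in which "AEs and SAEs are assigned to the following phases: Screening", each treatment group, and post-treatment for each group.

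SAP 7.8.1.7 takes time at risk for a patient with an AE as "date of start of AE with specified PT/SOC/HLT – study treatment start date + 1".

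**The concern.** Under Protocol 5.3.7.2, AEs are collected from consent, and the synopsis allows 4 to 28 days of screening. A patient can therefore start trial medication with an AE already open. If that AE becomes more severe or serious on drug, the protocol calls it treatment-emergent, while the SAP as worded files it as pre-treatment. The two governing documents classify the same event differently.

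At stake are the main descriptive safety outputs in SAP 7.8.1.2: overall AEs, AEs by intensity, SAEs and AEs leading to discontinuation. These are the tables a reader would use to judge tolerability, and a change in their defining rule should be visible.

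**Working it through.** The plan states no figure to reproduce, so the check compares the rules and applies the SAP's own formula.

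**1. Time route.** Both documents use start of treatment to last dose + 7 days. They agree.

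**2. Deterioration route.** It is present in Protocol 7.3.4 and absent from SAP 7.8.1.1. The SAP is not merely silent, because it gives a positive rule for all AEs before first intake, and that rule has no exception.

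**3. Declared changes.** SAP Section 4 lists five changes: the baseline eGFR by time term, the end of time at risk for efficacy, the condensed MMRM, the win ratio rules and categorical LVEF. None concerns AEs. The SAP history table records safety-strategy changes to 7.8.1 in October 2019 and censoring clarifications to 7.8.1.1 in June 2020. Neither entry mentions this rule.

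**4. Meaning of occurring before.** The SAP does not say onset before. Reading it as onset is an inference, supported by the use of the AE start date in SAP 7.8.1.7.

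**5. Time-at-risk formula.** For an AE that starts k days before first intake, time at risk = -k + 1 = 1 - k days.
- k = 1: 0 days
- k = 4: -3 days
- k = 28: -27 days

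Under its original onset date such an AE cannot enter the rate calculation. This shows only that the SAP makes no provision for these events. The formula is meant for the on-treatment phase, so it is not a separate error.

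**6. What happens to a worsening in practice.** There are two cases.
- *Entered as a new occurrence with its own date.* Protocol 5.3.7.2 asks for worsening of a condition the patient already has to be recorded as an AE or SAE. SAP 7.8.1 merges occurrences only if every attribute matches, including intensity and seriousness. The new occurrence starts on treatment and is counted.
- *Kept under the original record and onset date.* SAP 7.8.1.1 makes it pre-treatment, and it does not reach the general tables.

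Neither document says which entry convention sites must follow.

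**7. Number affected.** This would need the proportion of patients with an AE open at first intake, the proportion of those that worsen on treatment, and the proportion kept under the original date. The documents give none of the three.

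**The case against.** The strongest reply is that nothing need be lost. The merging rule in SAP 7.8.1 covers adjacent occurrences with differing attributes, which suggests an eCRF that splits an AE when its intensity or seriousness changes. No passage describes a site overwriting the original record. This stands as a limit on the consequence, but it does not remove the conflict, because separate entry is nowhere required.

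A second reply is that the SAP says it elaborates Section 7 of the protocol and refers to sponsor guidance for AE summarisation, which may contain the rule. That guidance was not available and cannot be relied on. If it did contain the rule, it would still sit against the explicit text of SAP 7.8.1.1.

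Third, other outputs give partial cover. Screening-phase AEs appear in the appendix by phase and in listings. Creatinine rises and eGFR shifts are tabulated from laboratory values whatever the AE onset. Infections present at screening are documented as history or baseline conditions, and symptomatic hypotension at Visit 1 or 2 is an exclusion. This is fair, but the appendix as worded shows screening as one phase, not split by arm.

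A reader might infer that worsening on drug is systematically removed from the safety tables, or that what is lost is specifically the drug-related part. The documents support neither. The loss depends on data entry, and they give no information on how worsening would differ between arms.

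**Conclusion.** The conflict is real and undeclared. Its consequence is conditional: a screening-onset AE that worsens on treatment can be left out of the main on-treatment tables only if it stays under its original onset date. This rests on reading the SAP's pre-treatment rule as an onset rule and on no overriding text in the unseen guidance. The size cannot be computed and may be near zero. Protocol 7.3.4 plans no hypothesis testing for safety, so no confirmatory result is touched. The point is worth correcting because a sentence or two settles it, not because a material distortion has been shown.

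**What to change.** Add to SAP 7.8.1.1: *AEs with onset before first drug intake that deteriorate, i.e. increase in intensity or become serious, between first intake and last intake + 7 days are assigned to the randomised treatment.* This wording stays within the protocol's criterion; an unchanged AE that leads to discontinuation has not deteriorated and is not brought in.

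In SAP 7.8.1.7, use the date of worsening as the AE start date for time at risk where it is recorded. Where it is not, include the event in the frequency counts only, since a worsening date is not shown to exist when a site updates the original record. It would help to state in the SAP how changes in intensity are entered in the eCRF. If the sponsor means to drop the protocol rule, that should instead be declared and justified in SAP Section 4.

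The cost is a small extra derivation and slightly higher AE counts in both arms.

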7.3.5 Pharmacokinetic analyses

Individual concentration-time data with descriptive statistics for empagliflozin trough concentrations will be presented in the clinical trial report.

7.3.6 Prespecified meta-analyses

On project level, meta-analyses are pre-specified. Data from this trial and a parallel trial in HFpEF patients (1245.110) will be pooled.

The statistical model will include trial as a covariate. More details are specified in the meta-analysis plans.

7.4 INTERIM ANALYSES

The safety and conduct of the trial will be monitored by an independent DMC. Details on this process are outlined in the DMC charter.

There will be one unblinded interim analysis to be conducted by the DMC. At the time of the interim analysis, the ExSC, SEC, Sponsor, CRO and all trial/site personnel will stay blinded to the interim results. For blinding, please also refer to [Section 4.1.5.1](#).

After approximately 500 primary adjudicated outcome events have been accrued (approximately 60% of information is available) an interim analysis will be performed.

The following Hwang, Shih and De Cani α -spending function for the analysis at information fraction t_k (planned to be approximately 60%) with parameter $\gamma = -8$ will be used:

$$\alpha^*(\gamma, t_k) = \min \left\{ \alpha, \quad \alpha \frac{1 - e^{-\gamma t_k}}{1 - e^{-\gamma}} \right\} = \min \left\{ 0.025, \quad 0.025 \frac{1 - e^{8t_k}}{1 - e^8} \right\}$$

The chosen alpha-spending function spends an alpha-level of 0.001 at the time of approximately 60% of information for the interim analysis.

If the p-value for the primary endpoint and the p-value for CV-death (from the primary Cox proportional hazards model) are lower than the cut-off to be evaluated from the alpha spending function (planned at 0.001 one-sided), the trial will be stopped for overwhelming efficacy. In this case, the hierarchy will be tested as specified in [Section 7.2](#). Otherwise the trial will be continued.

The final alpha level is therefore planned at a one-sided alpha-level of 0.0248 which translates in a two-sided alpha of 0.0496.

The event rate will be assessed by the trial team in a blinded manner only during trial recruitment and before the unblinded interim analysis (see [Section 7.7](#)).

7.5 HANDLING OF MISSING DATA

There will be no imputation for safety data or for time-to-event type of endpoints. For patients who discontinue the trial treatment prematurely, all efforts will be made to follow the patients for survival and any other endpoints, including the primary and key secondary endpoints, until the end of the trial.

For the slope analysis of eGFR (CKD-EPI)_{cr}, all available on-treatment change from baseline data will be used. Patients without on-treatment data after randomisation will not be included in this analysis.

For the analysis of change from baseline to 30 days after treatment stop, only available data will be used. Only patients with post-treatment data will be used in this analysis.

For other longitudinal efficacy endpoints such as KCCQ scores, MMRM methodology will be used. Models will be run on both all observed data and all observed on-treatment data. Details of the imputation rule will be given in the statistical analysis plan.

An eGFR (CDK-EPI) reduction is considered sustained, if it is determined by two consecutive post-baseline central laboratory measurements separated by ≥ 30 days. If only one post-baseline value is available and the patient dies within 60 days of this measurement without second measurement ≥ 30 days after the first, then the eGFR reduction is also considered sustained.

7.6 RANDOMISATION

The trial will be performed as a double-blind design with respect to placebo and empagliflozin. Subjects will be randomised to the trial treatments in a 1:1 ratio. The randomisation will be stratified by the following factors:

- Geographical region (North America, Latin America, Europe, Asia, Other)
- Status of DM at screening :

- no DM (HbA1c < 5.7% without the intake of antidiabetic medication, unless taken for a non-DM indication, and no history of DM) or
 - pre-DM (HbA1c \geq 5.7% and <6.5% without the intake of antidiabetic medication, unless taken for a non-DM indication, and no history of DM) or
 - DM (HbA1c \geq 6.5%, or intake of antidiabetic medication for a DM indication, or history of DM)
- and eGFR (CKD-EPI)cr at screening
 - <60 mL/min/1.73m²
 - \geq 60 mL/min/1.73m²

Patients will be randomised in blocks to double-blind treatment via an IRT system. Approximately equal numbers of patients will be randomised to each treatment group. BI will arrange for the randomisation and the packaging and labelling of trial medication. The randomisation list will be generated using a validated system, which involves a pseudo-random number generator so that the resulting treatment will be both reproducible and non-predictable. The block size will be documented in the Clinical Trial Report (CTR). Access to the codes will be controlled and documented.

7.7 DETERMINATION OF SAMPLE SIZE

For the sample size calculation, a yearly event rate in the placebo group of 15% is assumed (ref. Paradigm 12% event rate [[R16-1460](#)], Rales 18 % event rate [[P99-02524](#)], and Emphasis-HF 15% event rate [[R16-1459](#)]). In the CHARM – added trial [[R06-0956](#)] event rate was 16.5%. The trial is designed to achieve a power of 90% for a two sided test at level $\alpha = 0.05$.

The following table ([Table 7.7: 1](#)) presents the number of required events together with the number of to be randomised and treated patients assuming an accrual period of 18 months and a follow-up period of 20 months for different assumed true hazard ratios. However, the follow-up period is not fixed but the trial will continue until the necessary number of events is observed, which are confirmed by the adjudication committee.

The drop-out rate from the trial is assumed to be very low (< 1% per year) and is therefore not further considered for the determination of sample size.

Table 7.7: 1 Sample size calculation without considering interim analysis

Yearly event rate for HHF+CV Death (placebo)	Hazard ratio	Number of events for 90% power for HHF+CV Death	Number of patients for 18 months accrual and 20months follow up
15%/Year	0.70	330	1178
15%/Year	0.75	508	1764
15%/Year	0.80	841	2850
15%/Year	0.85	1591	5268
15%/Year	0.90	3786	12256

A hazard ratio of 0.8 was chosen as a conservative estimate based on the results of EMPA-REG OUTCOME” described in [Section 1.2.3](#)

Therefore, at least 841 confirmed primary events should be observed and at least 2850 patients should be randomised and treated in order to achieve a power of 90% assuming a true hazard ratio of 0.8.

Including interim analysis with Hwang-Shih-deCani alpha spending with $\gamma=8$ at 60% of information will decrease the power only slightly (>89.5%).

The blinded event rate and recruitment progress will be assessed during recruitment before any interim unblinding. If the accumulated data suggests a slower accrual of primary outcome events over calendar time than originally projected, then the number of randomised patients may be increased to a maximum of 4000 patients. Operationally, the recruitment period would be extended and could continue up to 6 months before the target number of events is expected to be achieved. The number of confirmed primary outcome events will not be affected by this consideration and will remain 841 events.

Calculations were performed using ADDPLAN6.1.1 by ADDPLAN Inc.

Based on the abovementioned assumptions, and considering that HHF (first and recurrent) will only be tested if the primary endpoint is successful, the chance of showing significance for HHF (first and recurrent) in a positive trial is at least 70%.

For the integration of a Japanese population in this global phase III trial, and in order to comply with the regulatory requirements for bridging the trial results to this population, the Japanese patients to be randomised will be followed and controlled if necessary. Approximately 118 patients are expected to be randomised to each treatment arm for the Japanese population.

8 INFORMED CONSENT, TRIAL RECORDS, DATA PROTECTION, PUBLICATION POLICY

The trial will be carried out in compliance with the protocol, the ethical principles laid down in the Declaration of Helsinki, in accordance with the ICH Harmonized Tripartite Guideline for GCP and relevant BI SOPs and CRO SOPs, the EU regulation 536/2014, the Japanese GCP regulations (Ministry of Health and Welfare Ordinance No. 28, March 27, 1997) and other relevant regulations.

Standard medical care (prophylactic, diagnostic and therapeutic procedures) remains in the responsibility of the treating physician of the patient.

The Investigator will inform the Sponsor/CRO immediately of any urgent safety measures taken to protect the trial subjects against any immediate hazard, and also of any serious breaches of the protocol or of ICH GCP.

The Boehringer Ingelheim transparency and publication policy can be found on the following web page: trials.boehringer-ingelheim.com. The rights of the Investigator and of the Sponsor with regard to publication of the results of this trial are described in the Investigator contract. As a rule, no trial results should be published prior to finalisation of the Clinical Trial Report.

For Japan only: The rights of the investigator/trial site and of the Sponsor/CRO with regard to publication of the results of this trial are described in the investigator contract / trial site's contract. As a general rule, no trial results should be published prior to finalisation of the Clinical Trial Report.

The certificate of insurance cover is made available to the Investigator and the patients, and is stored in the ISF.

